9.4.2 Termination of the entire study

If the suspected case of a serious unexpected adverse reaction occurs during the human study after taking 15 mg β -carotene plus placebo, 15 mg β -carotene with 25 mg iron (FeSO4), and 15 mg β -carotene with 30 mg zinc (ZnSO4), the study will be terminated at any time for the benefit and in the interest of the subjects. In this case, the Ethics Committee would be informed immediately.

10 Data collection and analysis

Statistical analysis will be performed by the study coordinator. Bioavailability will be determined by the area under the curve (AUC), maximum plasma concentration (Cmax), and time to reach Cmax (Tmax) of β -carotene. Significant differences between interventions will be determined using GraphPad Prism 6.0 software using one-factorial analysis of variance for repeated measures.

11. amendments to the protocol.

The applicants are aware that the vote of the Ethics Committee covers only the information contained in the application and does not include extensions and changes to the research proposal made at a later date. The applicants are aware that in case of changes, a protocol annex is required, which must be signed by the study directors, and that all protocol changes must be reported to the Ethics Committee. The applicants are aware that a new vote of the Ethics Committee must be obtained for protocol changes that are not exclusively formal in nature and that contain changes relevant to the study participants. Potential changes in study conditions would be brought to the attention of study participants during the informed consent process.

12 Ethical and legal issues

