3.1 Target parameters and evaluation

The bioavailability of β -carotene is determined via the measured plasma and chylomicron concentrations by HPLC (see 8.6 Methods). For this purpose, ultracentrifugation is used to isolate the chylomicron fraction and extract β -carotene. Pharmacokinetics for plasma and chylomicron fraction are calculated using the area under the concentration-time curve. This quantity can be used to quantify the bioavailability of β -carotene in comparison between single and combined intakes. Statistical analysis is performed using one-factor analysis of variance.

4. study population

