4.1 Number of subjects

The required power for the study will be calculated based on the area under the plasma concentration-time curve (AUC). Study power is calculated based on the following formula: n > F (σ /d)2, where n = number of subjects, σ = standard deviation of the dependent primary outcome measure, d = difference between control and treatment classified as significantly different in the literature. The corresponding F-values can be found in the table below; for the planned study, P < 0.05 and 90% power are assumed, resulting in an F-value of 10.51 (Scales & Rubenfeld 2005).

	Power			
Significance level (P-value)	80%	90%	95%	99%
0.100	6,18	8,56	10,82	15,77
0.050	7,85	10,51	12,99	18,37
0.025	9,51	12,41	15,10	20,86
0.010	11,68	14,88	17,81	24,03

F-value Table:

In a comparable study by (Goltz et al. 2013), an AUC of 22.6 \pm 7.6 [nmol*L-1*h] could be determined after intake of 20-30 mg β -carotene (n=6). This results in a mean value of 22.6 nmol*L-1*h and a standard deviation of 7.6 nmol*L-1*h. A reduction of bioavailability by more than one third would represent a biologically relevant effect, which is why a significant difference of rounded up 35%, corresponding to 7.9 nmol*L-1*h, is used for the calculation in this study. Thus, n > 10.51 x (7.6/7.9)2 results in a number of at least 9.7, rounded up to 10 subjects. To allow for a balanced experimental design in which all permutations of the timing of the interventions occur in equal numbers, a total of 12 healthy males aged 18-45 years will be recruited for this study. Females will be excluded from the study because the menstrual cycle affects blood concentrations of carotenoids (Forman et al. 1998).

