4.2 Duration of the study

The duration of the study is approximately 3 weeks per subject and includes 3 interventions, each preceded by a 1-week washout period. The three interventions each consist of a single oral administration of 15 mg β -carotene with placebo, in combination with 25 mg iron (FeSO4), or in combination with 30 mg zinc (ZnSO4).

5. selection of subjects

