8.3 Nutrition

Standardized meals will be served on the study days (from the evening before the intervention until the collection of the 10 h blood sample). Subjects will be instructed not to consume foods containing β -carotene (see Subject Information and Supplementary Information) during the studies. An appropriate list of foods and beverages to be avoided will be given to subjects as part of the subject information.

The standardized meals are composed as follows:

Dinner before the first study day consists of farmhouse bread with butter and camembert, plus roasted macadamia nuts and natural yogurt without artificial colors or additives. For breakfast on the study day, fresh wheat rolls with cream cheese (natural) and Greek yogurt are served in parallel with taking the capsules. Lunch on the study day is served four hours after taking the capsules and consists of pasta with cheese sauce, rolls and yogurt ice cream for dessert. The snack 6 hours after intervention consists of ricotta cake. For dinner on the study day, potato salad, farmhouse bread with butter, almonds, and a yogurt are served. All foods used were chosen from the point of view of avoiding additional intake of β -carotene.

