8.5 Experimental procedure

Subjects are considered to be enrolled in the study if all inclusion criteria have been met during screening (see section 5.1), none of the exclusion criteria (see section 5.2) are present and the subjects have given their written consent to participate in the study.

On the evening before the intervention, subjects will receive a standardized meal and a standardized snack for consumption between dinner and 10 pm. Subjects will be asked to drink only water and consume no other food after 10 pm and until the intervention on the day of the trial. On the morning of the trial day, subjects will receive a single oral dose of 15 mg β -carotene plus placebo, 15 mg β -carotene combined with 25 mg iron (FeSO4), or 15 mg β -carotene combined with 30 mg zinc (ZnSO4) after breakfast. Standardized meals will be served to study participants throughout the day of the intervention. Blood samples will be collected at baseline (0 h) and 1, 2, 3, 4, 5, 6, 7, 8, 9, and 10 h after ingestion of the study drugs (11 blood samples). A total of approximately 120 mL of blood will be collected per intervention.

As the study is a cross-over study with three arms, after each 1-week washout period, the same experimental procedure is performed in random order with one of the remaining study preparations each time.

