9.4 Discontinuation criteria

9.4.1 Discontinuation of the study in one subject (drop-out).

The study is discontinued in an individual subject if the subject withdraws consent to participate in the study, the study protocol is violated, an exclusion criterion or disease occurs, or other circumstances arise that would jeopardize the subject's health if the subject continued to participate in the study.

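### The planned one-factor repeated-measures ANOVA leaves period out of a three-period crossover: lost precision if all 12 men complete, possible bias if men are withdrawn and visits differ

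*Combined protocol and SAP*

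**What the plan says.** Section 8.5 gives the design: "As the study is a cross-over study with three arms", with the three preparations taken in random order. Section 4.1 calculates 10 subjects and raises this to 12 for a stated reason: "To allow for a balanced experimental design in which all permutations of the timing of the interventions occur in equal numbers". Three preparations have six orders, so 12 men give two per order.

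The analysis appears twice. Section 3.1 (Target parameters and evaluation) says: "Statistical analysis is performed using one-factor analysis of variance". Section 10 is more specific: "Significant differences between interventions will be determined using GraphPad Prism 6.0 software using one-factorial analysis of variance for repeated measures". Neither sentence names period, visit or sequence, and no other section does. The outcomes are AUC, Cmax and Tmax (section 10), with AUC in two matrices: "Pharmacokinetics for plasma and chylomicron fraction are calculated using the area under the concentration-time curve".

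Two features of the conduct bear on visit-to-visit differences. Section 4.2 says the study "includes 3 interventions, each preceded by a 1-week washout period", and section 8.3 says: "Standardized meals will be served on the study days".

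Men can leave early. Section 9.4.1 begins: "The study is discontinued in an individual subject if the subject withdraws consent to participate in the study", and goes on to protocol violations and illness; section 9.2 also removes a man after a study-related event. No replacement rule is given, and nothing says how a man with one or two completed visits is analysed.

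**The concern.** The plan adds two men so that treatment order is balanced over visits, then analyses the data with a model that has no place for visits. Balance protects the treatment estimates; it does not remove a shared visit effect from the residual. If AUC moved up or down from visit 1 to visit 3 in all men alike, that movement would be counted as error. The intervals would be wider than they need be, and the test would reject less often than its nominal level.

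The protection of the estimates also depends on the balance surviving. In a trial of 12 with two men per order, one or two withdrawals leave the orders unequal. Under the one-factor model, part of a visit effect can then appear as a treatment difference.

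**Working it through.** **Inputs from section 4.1.** Mean AUC 22.6, SD 7.6, planned difference 7.9 (35% of 22.6), all in nmol·h/L; two-sided 5% level; 12 men.

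**The plan's own figure.** 10.51 × (7.6/7.9)² = 9.73, so 10 subjects. The plan's 9.7 reproduces.

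**Assumptions not in the documents.** (a) Within-subject SD s. The plan gives none, so two readings are shown: s = 7.6/√2 = 5.37 (7.6 as the SD of a paired difference, or as a total SD with correlation 0.5) and s = 7.6. (b) A linear drift of d per visit, the same in every man. (c) One mineral lowers AUC by 7.9; lowering both gives the same noncentrality. Subject is fitted as fixed.

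**Degrees of freedom.** There are 36 observations. Subject and treatment use 12 + 2, leaving 22 for error; period takes two more, leaving 20. With 12 completers the variance of a treatment contrast is s² × 2/12 under either model.

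**Power of the omnibus F test, 12 completers.**
- Treatment noncentrality: 12 × (2/3) × 7.9²/s² = 8 × 62.41/s², which is 17.29 (s = 5.37) or 8.64 (s = 7.6).
- Without period, the drift adds noncentrality 12 × 2d²/s² = 24d²/s² to the 22-df denominator. At d = 2.26 this is 4.24 or 2.12.
- With period: noncentral F on 2 and 20 df, unaffected by d.

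| Drift per visit, % of 22.6 | Shift, visit 1 to 3 | s = 5.37: without / with period | s = 7.6: without / with period |
|---|---|---|---|
| 0 | 0 | 94.4 / 94.1 | 68.9 / 68.3 |
| 5 | 2.3 | 93.7 / 94.1 | 67.8 / 68.3 |
| 10 | 4.5 | 91.1 / 94.1 | 64.6 / 68.3 |
| 17.7 | 8.0 | 81.8 / 94.1 | 55.6 / 68.3 |

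The two models break even at d = 0.74 (3.3% of 22.6) for s = 5.37 and d = 0.88 (3.9%) for s = 7.6. The loss reaches 10 points only at d = 3.69 or 3.56, a shift of 7.4 or 7.1 from visit 1 to visit 3.

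**Type I error without period.** At 10% drift per visit the nominal 5% test rejects a true null in 3.0% (s = 5.37) or 3.9% (s = 7.6) of trials.

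**Interval width, s = 5.37.** Without period the error mean square is about (22s² + 24d²)/22. The 95% half-width of a mineral-minus-control difference is 4.55 without and 4.58 with period at no drift, and 4.97 against 4.58 at 10% per visit.

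**Withdrawal, complete cases, one-factor model.** Over all 12 men, the visit differences between a mineral and control sum to zero. A man who took the mineral at visit 1 and control at visit 3 contributes −2d. If two such men are lost, the other ten sum to +4d, a bias of 4d/10 = 0.4 × 2.26 = 0.90, and 0.90/7.9 is about 11%. This is the largest value for two lost men; other pairs give less, and some give zero. Fitting period removes it.

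**The case against.** The strongest reply is that the design already deals with period. Equal use of all orders removes period bias from every contrast when all 12 men complete, and one-factor repeated-measures ANOVA is then a valid analysis. Washouts and standardised meals work against a drift, and no section reports one. Below the break-even drift the added term loses power, and a 10-point loss needs a visit 1-to-3 shift nearly as large as the planned effect. Only linear drift was examined.

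Most of this stands, and it limits the point to a minor one. It does not remove it. The documents do not exclude a drift either: each visit follows a further week of low-carotenoid diet and, after the first, an earlier 15 mg dose, and neither analysis passage says that AUC is corrected for the 0 h value. The argument from balance also fails once men are withdrawn.

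Three stronger readings are tempting, and the documents do not support them.
- *The plan as designed is biased or prone to false positives.* With 12 completers it is neither: contrasts are unbiased, and a drift pushes the rejection rate below 5%.
- *Section 3.1 plans an unpaired ANOVA.* Its wording is a shorter form of section 10, which specifies repeated measures. The two should match, but they do not conflict.
- *A drift of the tabulated size is expected.* Every drift value above is an assumption.

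**Conclusion.** The point holds as a minor one. A factor that the design balances is missing from the model. With 12 completers the consequence is a conditional loss of precision and a conservative test; with withdrawals, a period effect can also bias the contrasts, by up to 0.9 nmol·h/L in the case worked above. Both depend on a visit effect whose existence and size the documents do not establish.

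The price of protection is small: 0.3 point of omnibus power at s = 5.37 and 0.7 at s = 7.6, with 12 completers and no period effect. These figures belong to the two assumed SDs. Higher within-subject correlation makes the cost smaller; for a single unadjusted mineral-versus-control contrast it is 0.2 to 0.4 point.

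**What to change.** State one model for AUC and Cmax, in the same words, in sections 3.1 and 10:

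> AUC (plasma and chylomicron fraction) and Cmax will each be analysed with a linear mixed model with treatment and period as fixed effects and subject as random effect, using all completed periods, with Kenward-Roger degrees of freedom. The treatment effect will be tested with its F test, and each mineral-minus-control difference will be reported with its 95% CI.

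Leave the Tmax analysis as section 10 has it. The degrees-of-freedom method needs naming because the sample is small and visits may be missing. The power figures above fit subject as fixed; with partial data a random-subject model can differ somewhat. Using all completed periods settles the separate question of partial data, a benefit that should not be credited to the period term.

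Cost: two error degrees of freedom. If there is no period effect, that is 0.3 to 0.7 point of power with 12 completers, 0.7 to 1.2 with 11 complete cases and 1.4 to 1.8 with ten. Beyond that, it needs software that fits the model, and a signed protocol annex reported to the Ethics Committee under section 11. No extra subjects or visits are needed.

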12.1 Legal basis

The study will be conducted in accordance with the Declaration of Helsinki (as amended) and the Guidance on Good Clinical Practice (GCP) Regulations.

12.2 Vote of the Ethics Committee

The applicants are aware that the prerequisite of the nutritional study is compliance with the guidelines and laws listed under item 12.1 and that the initiation and conduct of the study are subject to the vote of the Ethics Committee. The Ethics Committee will be informed immediately in the event of serious events (section 9.3), study termination (section 9.4) and protocol changes (section 11). After completion of the study, the Ethics Committee will be provided with a report and, if necessary, a publication.

12.3 Documentation, archiving and data protection

The recording of the collected findings is done by means of a test sheet. Among other things, the test sheet will summarize information about the participating person in pseudonymized form (ID number), information about which 15 mg β -carotene with placebo capsule, 15 mg β carotene with 25 mg iron (FeSO4) and 15 mg β -carotene with 30 mg zinc (ZnSO4) preparation the person received, findings of the blood test, etc.

All data collected in the study will be subject to data protection and will be kept strictly confidential. Samples will be encrypted and no report or publication will reveal the identity of study participants. Blood samples will leave the facility in encrypted form. The transfer of test forms and data storage for evaluation will only be done with the anonymized data of the study participant. Assignment of personal data to study data will be made only by the study director. After completion of the study, the data will be stored for a period of 10 years.

Literature

Forman, M.R. et al., 1998. Effect of menstrual cycle phase on the concentration of individual carotenoids in lipoproteins of premenopausal women: A controlled dietary study. American Journal of Clinical Nutrition, 67(1), pp.81–87.

Goltz, S.R. et al., 2013. Carotenoid bioavailability from raw vegetables and a moderate amount of oil in human subjects is greatest when the majority of daily vegetables are consumed at one meal. Nutrition Research, 33(5), pp.358–366. Available at: http://dx.doi.org/10.1016/j.nutres.2013.02.010.

Goltz, S.R. et al., 2012. Meal triacylglycerol profile modulates postprandial absorption of carotenoids in humans. Molecular Nutrition and Food Research, 56(6), pp.866–877.

